4.1 Primary objective

The primary study endpoint is the change in severity of urinary symptoms over time as determined by the IPSS questionnaire score, specifically comparing the symptoms at the 1st BCG treatment (baseline) to the symptoms at the 6th week of treatment. The difference in the degree of urinary symptoms between the placebo and genistein supplement arms will help reflect whether genistein supplement can improve the quality of life in BCG intravesical therapy patients.

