4.2 Secondary objective

- a) A secondary study endpoint will be the presence of cancer and the rate of recurrence as determined by the 10-week biopsy or subsequent standard follow-up visits.
- b) A second secondary study endpoint will be the total dose of intravesical therapy administered over the 6 weeks of treatment. If subjects develop fewer urinary tract symptoms as a result of the genistein supplement, then hypothetically, intravesical therapy dosing would not have to be reduced as much. This will be measured by looking at the level of dose reduction for each treatment week and comparing it across the two arms.

5. Study Design and Methods:

At the pre-operative office visit before intravesical therapy, eligible patients will be screened and enrolled into the study by going through the consent process and signing the consent and HIPAA forms. Each patient will need to report all other medications so that the study team can assess whether certain medications might affect trial outcome.

Patients will be randomized into Arm 1 (placebo) or Arm 2 (genistein supplement) at a ratio of 1:1 stratified by one dichotomized prognostic factor, age. The dichotomization will take place based on whether they are age 60 and above or whether they are age 59 and below. This will allow for similar age groups to be placed in each arm, so that the degree of urinary symptoms while receiving treatment is not skewed depending on the patient's age.

Patients are treated with intravesical therapy once a week for 6 weeks and then return to the office approximately four weeks later for a post-operative visit and biopsy, as is standard care. Study subjects will take their genistein or placebo tablets for a total of 10 weeks, which includes the length of their treatment, as well as the 4 weeks before the post-op visit. Each patient will fill out an International Prostate Symptom Score (IPSS) questionnaire at their baseline office visit when consented. Patients will fill out an IPSS questionnaire at each subsequent intravesical therapy session and their final one-month follow-up appointment (at 10 weeks) either in person or via phone call with a study team member. The IPSS questionnaire will gauge their urinary symptoms throughout their therapy and provide measurable symptom scores for the two arms. The biopsy at 10 weeks, as well as standard 3 months follow-up appointments, is standard care for superficial bladder patients and will help determine cancer rate of recurrence.

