	Baseline	BCG Week 1-6 ^b	10 Week ^c
Placebo Arm	
 • Screening (Physical Exam,^a Vitals,^a complete blood count and serum chemistry analyses, ^a Urine Dipstick, IPSS Questionnaire) • Enrollment • Randomization 	
 • Urine Dipstick, Interval History, Vitals, IPSS Questionnaire* • BCG Intravesical Therapy • 6 weeks of placebo (30 mg, PO TID) • Continue taking placebo for remaining 4 weeks before biopsy 	
 • Bladder Cystoscopy (Biopsy recommended, but not mandatory) • Urinary cytology (if indicated) • Interval History • IPSS Questionnaire* • Physical Exam • Vital signs • Complete blood count and serum chemistry panel is recommended, but not mandatory
Genistein Supplement Arm	
 • Screening (Physical Exam, ^a Vitals,^a complete blood count and serum chemistry analyses, ^a Urine Dipstick, IPSS Questionnaire) , • Enrollment, • Randomization 	
 • Urine Dipstick, Interval History, Vitals, IPSS Questionnaire*, • BCG Intravesical Therapy • 6 weeks of genistein Supplement (30 mg, PO TID) • Continue taking genistein Supplement for remaining 4 weeks before biopsy 	
 • Bladder Biopsy (pathology) • Urinary cytology • Interval History • IPSS Questionnaire* • Physical Exam • Vital signs • Complete blood count and serum chemistry panel is recommended, but not mandatory

^a Within 2 months before the first dose of study treatment.

^b A range of 7 days before or after the scheduled visit is allowed or per standard of care. If BCG treatment is interrupted or discontinued Urine Dipstick, Interval History, and Vitals may not be collected per standard of care.

^c A range of 2-3 weeks before or after the 10 week is allowed or per standard of care.

*IPSS Questionnaire may be collected via phone call.

6. Participant Selection:

44 patients will be enrolled in the trial, with 22 subjects on each arm. Potential subjects will be superficial bladder cancer patients in the Department of Urology who are scheduled for their standard-of-care BCG intravesical therapy.

Inclusion Criteria:

1. Male or female gender
2. 18 years or older
3. Diagnosis of superficial bladder cancer
4. Scheduled for induction BCG intravesical therapy
5. Willing and able to give blood sample
6. Willing and able to fill out a pill diary to ensure compliance
7. Willing and able to sign informed consent

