8.2 Statistical analysis plan

8.2.1 Primary analysis

The IPSS score change at 6-week from baseline will be calculated with 95% confidence interval and compared between two experiment groups through Mann-Whitney test. The baseline, minimum three treatment period IPSS scores, and the 10-week biopsy IPSS scores are required in order for the patient to be evaluable.

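### Section 4.1 and Section 5 place the baseline IPSS at different visits, so two primary change scores are possible; one must be named, and adjusting for it is an optional gain

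*Combined protocol and SAP*

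**What the plan says.** Section 4.1 (primary objective) compares week 6 with "the symptoms at the 1st BCG treatment (baseline", the parenthesis being the protocol's own label.

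Section 5 (study design) puts the baseline questionnaire elsewhere. Enrolment comes first: "At the pre-operative office visit before intravesical therapy, eligible patients will be screened and enrolled into the study". Each patient then completes an IPSS "questionnaire at their baseline office visit when consented", and after that "Patients will fill out an IPSS questionnaire at each subsequent intravesical therapy session".

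The schedule table agrees with Section 5. Its Baseline column includes "Urine Dipstick, IPSS Questionnaire" among the screening items, and its BCG Week 1-6 column includes "Urine Dipstick, Interval History, Vitals, IPSS Questionnaire". Both a consent score and a first-session score are thus planned for every patient.

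The table's two-month window before first study treatment is attached to the physical exam, vitals and blood tests, not to the IPSS. The documents do not say whether the first-session IPSS comes before the first instillation or the first study tablet.

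Sections 8.1 and 8.2.1 use the word baseline without naming a visit. The primary analysis in 8.2.1 is worded: "The IPSS score change at 6-week from baseline will be calculated with 95% confidence interval and compared between two experiment groups through Mann-Whitney test". The evaluability rule in 8.2.1 reads "The baseline, minimum three treatment period IPSS scores, and the 10-week biopsy IPSS scores are required", so it lists baseline apart from the treatment-period scores.

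**The concern.** The primary endpoint is a difference between two scores, and the plan defines one of them in two ways. An analyst working from 4.1 would subtract the first-session score. One working from Section 5, the table and the evaluability wording would probably subtract the consent score. In a trial of about 40 evaluable patients the two can differ enough to move a p-value across 0.05.

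Three things depend on the answer: the reported primary result; the meaning of the SD of 3.5 and the 83% power in 8.1, which describe one change score and need not hold for the other; and who is evaluable, because a first-session score might serve as baseline, as one of the three treatment-period scores, or as both.

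A second, lesser matter is that the primary test uses baseline IPSS only by subtraction and does not use the age stratum from the randomisation. That is an efficiency left unused, not an error.

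**Working it through.** **Inputs from 8.1.** 20 per arm; mean change +6 against +3, so a difference of 3; SD of change 3.5; one-sided 0.05; Mann-Whitney. The documents give no correlations, so all of those below are assumptions.

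**1. The plan's own figure.** Take noncentral t power with n multiplied by the Mann-Whitney efficiency 3/π.
- Effective n = 20 × 3/π = 19.1 per arm.
- Noncentrality = 3 / (3.5 × √(2/19.1)) = 2.65 on 36.2 df.
- Power = 83.0%; simulation gives 82.3%. The stated 83% is reproduced.
- The unadjusted t-test has noncentrality 3 / (3.5 × √0.1) = 2.71 and power 84.5%.

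**2. Two change scores from the same trial.** Let r be the correlation of either baseline with week 6, and ρ the correlation between the two baselines. With equal variances, the two change scores correlate (1 − 2r + ρ) / (2(1 − r)). For example, r = 0.5 and ρ = 0.9 gives 0.90; r = 0.7 and ρ = 0.6 gives 0.2/0.6 = 0.33. Both changes have SD 3.5. Simulation, 60,000 trials per cell:

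| | ρ = 0.6 | 0.7 | 0.8 | 0.9 |
|---|---|---|---|---|
| Tests disagree at 0.05, true difference 3: r = 0.5 | 19.4% | 16.7% | 14.1% | 10.2% |
| r = 0.6 | 21.3% | 18.3% | 15.5% | 11.4% |
| r = 0.7 | 24.5% | 21.5% | 17.8% | 13.2% |
| Either significant, no true effect: r = 0.5 | 8.4% | 8.1% | 7.4% | 6.8% |
| r = 0.6 | 8.6% | 8.2% | 7.7% | 7.0% |
| r = 0.7 | 8.8% | 8.4% | 8.1% | 7.3% |

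In the four corner cells, about 71% to 93% of the disagreeing trials had a non-significant p below 0.15. One test significant while the other mean difference was reversed occurred in at most 0.3% of trials.

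**3. Power if the two scores differ in quality.** With the same IPSS SD σ at each visit, SD of change = σ√(2(1 − r)). Write the correlation with week 6 as consent / first session.
- SD 3.5 belongs to the first-session change, 0.5 / 0.7: σ = 3.5/√0.6 = 4.52; consent change SD = 4.52 × √1.0 = 4.52; power about 64%.
- Same, 0.8 / 0.7: consent change SD = 4.52 × √0.4 = 2.86; power about 94%.
- SD 3.5 belongs to the consent change, 0.5 / 0.7: σ = 3.5/√1.0 = 3.5; first-session change SD = 3.5 × √0.6 = 2.71; power about 96%.

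The unnamed choice can thus move power either way.

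**4. Adjustment.** With the SD of change held at 3.5, equal variances and normal scores, the ANCOVA residual SD is 3.5 × √((1 + r)/2). Baseline IPSS and age stratum take the df from 38 to 36.

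| r | Residual SD | Noncentrality | One-sided power |
|---|---|---|---|
| 0.3 | 2.82 | 3.36 | 95% |
| 0.5 | 3.03 | 3.13 | 92% |
| 0.7 | 3.23 | 2.94 | 89% |
| 0.9 | 3.41 | 2.78 | 86% |

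Of the gain over 83.0%, 84.5 − 83.0 = 1.5 points is t against rank efficiency, not adjustment. When the slope of week 6 on baseline is near 1 (week-6 SD 1.4 times the baseline SD, r = 0.7), simulated power is 84.1% for ANCOVA and 82.8% for Mann-Whitney, so almost nothing is gained. No gain is claimed for age.

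**The case against.** The strongest reply is that 4.1 is the only place that defines the endpoint. It names both time points, so baseline in 8.2.1 can be read as taking that meaning, with Section 5 and the table describing visits. The evaluability wording can also be made to fit a first-session baseline. This has some force and makes the repair simple. It does not settle the matter: no rule of precedence is given, Section 5 and the table attach the word baseline to another visit, and a separately listed baseline sits more easily with the consent score.

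Stronger readings are tempting, and the objections to them stand.
- A reader might infer that the two baselines lead to opposite conclusions. The simulations show mostly near misses around 0.05 and almost never a reversed effect.
- A reader might infer from the 50%-accrual review in Section 10, which looks at data and questionnaires, that the type I error is already inflated. The actions stated there concern toxicity, biopsies and compliance; nothing has the reviewers testing or choosing the primary change score. The 7% to 9% applies only if someone chooses after seeing data.
- A reader might infer that a consent baseline costs power. Step 3 shows that a gain is equally possible, and the documents give nothing to decide between them.

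On adjustment, one may say that the planned test is valid, that ANCOVA is a preference, and that 8.2.2 c) already plans a GEE model of repeated IPSS. The first is true. But the adjustment uses data already collected, and the GEE model is exploratory and does not list the age stratum. The gain should not be oversold: normal scores favour ANCOVA, and r = 0.3 implies an IPSS SD of only 3.5/√1.4 = 2.96, half the assumed placebo rise of 6.

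**Conclusion.** The inconsistency is in the current text and affects the primary endpoint, so it should be corrected. It does not invalidate the design: either change score gives a valid randomised comparison if named in advance, and the 83% is right for whichever change has SD 3.5.

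The size, about 10% to 25% disagreement and a 7% to 9% error under a data-driven choice, rests on assumed correlations of 0.5 to 0.7 with week 6 and 0.6 to 0.9 between baselines, equal SDs and normal scores. Confidence in the contradiction is high; confidence in these magnitudes is moderate.

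The lack of covariate adjustment is not a fault. Adding it is a low-cost improvement whose benefit ranges from substantial at low r to small at high r or with a slope near 1.

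**What to change.** **(a) Needed.** Before unblinding, name one baseline visit in 4.1, Section 5, the schedule table and 8.2.1, and state when its IPSS is completed relative to the first instillation and the first study tablet. If it is the first-session score, say whether that score also counts toward the three treatment-period scores. If it does, a patient with scores from sessions 1 to 3 alone has two after baseline; Section 9 allows later scores by phone once BCG stops, so more may exist. No separate rule for a missing baseline is essential, because 8.2.1 already makes such a patient non-evaluable, but the visit must be named for that rule to work. Use the other score only in a labelled sensitivity analysis. Cost: wording in four places and no new data.

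**(b) Optional.** Pre-specify an ANCOVA of week-6 IPSS on arm, the named baseline IPSS and the age stratum, as the primary or as a supporting analysis, and report the adjusted difference with its interval. This does not replace (a), since the covariate needs the same definition. Cost: one model on data already collected, a linearity assumption and two degrees of freedom.

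### The evaluability rule in 8.2.1 does not match the week-6 primary endpoint: it can discard observed baseline-to-week-6 changes, and nothing covers a missing week-6 score

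*Combined protocol and SAP*

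**What the plan says.** Section 4.1 sets the primary endpoint as change in IPSS, "specifically comparing the symptoms at the 1st BCG treatment (baseline) to the symptoms at the 6th week of treatment". Section 8.2.1 follows it: "The IPSS score change at 6-week from baseline will be calculated with 95% confidence interval", with a Mann-Whitney comparison of the arms. Evaluability is then set on other data: "The baseline, minimum three treatment period IPSS scores, and the 10-week biopsy IPSS scores are required in order for the patient to be evaluable".

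Other parts of the protocol bear on this rule:

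- **Section 9** adds a condition of at least three BCG instillations for evaluability. It then provides for IPSS by telephone when BCG is interrupted or stopped. It also says that BCG is modified with the aim of relieving toxicity.
- **Section 5, text:** "Each patient will fill out an International Prostate Symptom Score (IPSS) questionnaire at their baseline office visit when consented". The visit table also places an IPSS under baseline screening. Section 4.1, by contrast, takes the first BCG treatment as baseline.
- **Section 5, visit table, 10 weeks:** the placebo column has "Bladder Cystoscopy (Biopsy recommended, but not mandatory"; the genistein column has "Bladder Biopsy (pathology" without that qualifier. Footnotes add "A range of 2-3 weeks before or after the 10 week is allowed or per standard of care" and "IPSS Questionnaire may be collected via phone call".
- **Section 8.1** allows 10% for drop-out or non-compliance, taking 44 patients to 40.
- **Section 8.2.2(c)** describes an exploratory GEE model of the repeated scores, with BCG dose as a predictor.

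The plan names no intention-to-treat set, no missing-data method and no sensitivity analysis for the primary endpoint.

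**The concern.** The change to be tested needs two scores, baseline and week 6. The rule asks for baseline, any three treatment-period scores and a score taken about four weeks after the endpoint. A measurement at week 10 cannot alter whether the week-6 change was observed, yet its absence removes the patient.

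The conditions that remove patients all arise after randomisation. Section 2 says that symptoms can begin after the first instillation, and Section 9 ties BCG changes to toxicity. Patients who stop early or miss visits may therefore be those with the worst symptoms. The trial's own hypothesis is that genistein lessens those symptoms, so such losses could fall more on placebo. At stake are the randomised comparison and, with 22 patients per arm, power. There is also a practical problem: two analysts could build different primary data sets from the same text.

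**Working it through.** **1. The rule against the endpoint.** Four cases, each with a baseline score:

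| Patient has | Week-6 change observed? | Meets the stated conditions? |
|---|---|---|
| All weekly scores, no 10-week score | Yes | No |
| Scores at weeks 1 and 6 only, plus week 10 | Yes | No, if these are the only treatment-period scores |
| Two instillations, later scores by telephone including weeks 6 and 10 | Yes | No, if Section 9 applies to the primary set |
| Scores at weeks 1, 2, 3 and 10, with three instillations | No | Yes |

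The first and last rows follow from 8.2.1 alone. The second also depends on the baseline definition, because a score at the first BCG session might serve as baseline, as one of the three, or as both.

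**2. The plan's power figure.** Inputs from Section 8.1: changes of 6 and 3, SD 3.5, 20 per arm, one-sided 0.05, Mann-Whitney. With the usual efficiency factor, n′ = 20 × 3/π = 19.1. Noncentrality is 3 / (3.5 × √(2/19.1)) = 2.65 on 2 × 19.1 − 2 = 36.2 df, giving power 83.0%. The stated 83% reproduces. Simulation of the test itself gives 86%, 82% and 79% at 22, 20 and 18 per arm.

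**3. Illustration of symptom-driven exclusion.** The documents give no exclusion rate, so the rates and correlations here are assumptions. Take 22 randomised per arm and no other loss. A patient is excluded when an early-symptom variable exceeds a common cut. That variable has correlation r with the week-6 change and the same standardised arm difference, 3/3.5 = 0.857. The cut is the placebo 95th, 90th or 80th percentile.

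Expected difference = 3 − r × 3.5 × (difference in truncated-normal means). For the 90th percentile the cut is 1.282 on the placebo scale and 1.282 + 0.857 = 2.139 on the genistein scale, which excludes 1.6% of genistein patients. The truncated means are −0.195 and −0.041, a difference of 0.154. So 3 − 0.3 × 3.5 × 0.154 = 2.84, and 3 − 0.5 × 3.5 × 0.154 = 2.73.

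| Excluded, placebo / genistein | Difference, r = 0.3 / 0.5 | Power, r = 0.3 / 0.5 |
|---|---|---|
| 5% / 0.6% | 2.90 / 2.84 | 83% / 82% |
| 10% / 1.6% | 2.84 / 2.73 | 80% / 79% |
| 20% / 4.5% | 2.74 / 2.56 | 75% / 72% |

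With no true effect, the same cuts give type I error of 4.8–5.0%.

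**4. Possible cost of keeping early stoppers.** Suppose that their symptoms subside and their change is 3 (assumed). The placebo mean is then (1 − p) × 6 + p × 3, and the difference is that minus 3: 2.85, 2.70 and 2.40 for p = 5, 10 and 20%. Power is 82, 78 and 68% with them included, against 85, 84 and 81% in evaluable patients only.

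**The case against.** **Few patients may be affected.** Section 2 describes dose reduction rather than stopping, scores can be taken by telephone, and the 10-week window is wide. This stands, and it is why the size is left open. Telephone contact limits missing scores, but it cannot restore a patient ruled out for too few instillations.

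**The 10% allowance already covers losses.** In part. It makes 82–83% the like-for-like comparator rather than 86%. On that basis 5% placebo exclusion costs almost nothing, 10% costs about 2 to 4 points, and only 20% is material (7 to 11 points). The allowance covers numbers. It does not address selective removal of observed outcomes or say what to do without a week-6 score.

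**Section 9's condition sits under adverse events.** True, so its reach over the primary test is not explicit. The mismatch in 8.2.1 stands without it.

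**The GEE model uses all scores.** It is exploratory and adjusts for BCG dose, which is itself post-randomisation.

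Three stronger readings are tempting but not supported:

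- *That the rule favours genistein or inflates type I error.* The route that the documents describe, symptom-driven change to BCG, attenuates a true benefit and leaves type I error near 5%. Inflation would need differential, outcome-related exclusion without a true effect, and the documents give no mechanism for that.
- *That patients without the endpoint are declared evaluable.* The conditions are worded as necessary, not sufficient. Such a patient might simply drop out of the test. The supportable claim is that no rule says so.
- *That the biopsy columns make exclusion differ by arm.* That would follow only if the 10-week score required a biopsy, and the table allows that score by telephone.

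**Conclusion.** The mismatch is certain from the text and should be fixed. The rule governing the primary test omits the one post-baseline score that the test uses, and it requires later or unrelated data instead. Observed primary outcomes can be discarded on post-randomisation grounds, and a missing week-6 score has no stated handling.

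The size is not known. Under the assumed exclusions in the working, the consequence ranges from negligible to a clear loss of power, with the expected difference falling from 3 to between 2.90 and 2.56. Those figures rest on normal changes, a common early-symptom cut, correlations of 0.3 to 0.5, and exclusion rates that appear nowhere in the documents. They illustrate direction and scale and do not forecast this trial. The sample-size calculation is not at fault.

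**What to change.** 1. Replace the evaluability sentence in 8.2.1. The primary analysis includes all randomised patients, in their assigned arm, with a baseline and a week-6 IPSS, whatever the 10-week score, the number of other weekly scores, the number of instillations or pill compliance. State that the three-instillation condition in Section 9 does not define this set.
2. Make week 6 the required score, taken by telephone if BCG has stopped, which the protocol already allows.
3. Keep the Mann-Whitney test and prespecify one simple handling of a missing week-6 score. One example is a supportive repeated-measures model of the weekly scores, with the week-6 contrast and without BCG dose as a covariate. Report missing week-6 scores and exclusions by arm, with reasons.
4. Report the current evaluable set as a supportive analysis.
5. Reconcile the baseline definition between Section 4.1 and Section 5 and use one for all patients. Call the later score the 10-week IPSS, without reference to biopsy, and reconcile the two biopsy entries in the visit table.

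**Cost.** SAP wording and a little more analysis; no new visits. The change is not free in power. Patients with little BCG exposure stay in and may dilute the contrast. In the scenario in step 4 of the working, that costs more power than excluding them, and power can fall below the planned 83%. The plan should say so. Including all randomised patients is a choice about what the trial estimates, and the supportive evaluable-set result lets readers see its effect.
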